12.1. Selection criteria

Inclusion

Human peripheral blood obtained from adult donors with the following characteristics:

- Patients with $\text{BMI} \geq 30\text{kg/m}^2$
- With risk factors for type 2 diabetes (history of diabetic parents or siblings, sedentary habits)
- Fasting blood glucose $\leq 126 \text{ mg/dL}$ or glycosylated hemoglobin $< 6.5\%$
- Controlled arterial hypertension
- >18 years of age
- Accept and sign the informed consent

No inclusion

- Hypersensitivity to the components of the formula
- History of hypoglycemic episodes
- History of obesity of endogenous origin
- History of serious psychological, psychiatric, eating or neurological disorders

- History of hyperthyroidism, heart disease, diabetes, liver or kidney failure, glaucoma, epilepsy
- Pregnancy or lactation

Exclusion criteria

- Pregnancy
- Diabetics
- Presenting any serious adverse effect
- Patients who decide to withdraw from the protocol

Elimination

- Samples contaminated during processing
- Lysed blood samples
- Coagulated blood simple.

Variable Description

Independent Variable

Berberine

Category: quantitative.

Measurement scale: ratio.

Measurement unit: 500 mg with excipient q.s.

Operational definition: the tested dose of Berberine was 500 mg, given to patients for 3 months.

Dependent

Gene expression of IL-1 β , TNF- α and NLRP3.

Category: quantitative.

Measurement scale: discrete, continuous.

Measurement unit: arbitrary units.

Operational definition: Cytokines were determined with commercial qPCR equipment/reagents, and their arbitrary units/relative expression were determined by a specific standard curve for each one.

Observation method: open.

Sampling method: non-probabilistic sampling of consecutive comparative groups that met the selection criteria, until reaching the sample size that constituted the study groups (patients with exogenous obesity).

Operational description of the study: Berberine has been provided by the Medix laboratory, in 500 mg capsules, to treat patients for 3 months.

Study groups

The individuals will be distributed into four groups:

- Group 1. Individuals with exogenous obesity: nutritional plan intervention for lifestyle change.
- Group 2. Individuals with exogenous obesity: nutritional plan intervention, moderate controlled aerobic exercise for lifestyle change.

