- Group 3. Individuals with exogenous obesity: nutritional plan intervention, moderate aerobic exercise and Berberine phytopharmaceutical. With biweekly sessions for 3 months.
- Group 4. Normal-weight individuals without intervention.

Blood samples were taken after informed consent from the participants, they were informed of the intervention and the group to which they belonged, they were also taken at the end of the study.

Procedure

In the selection, obtaining information, anthropometry and blood biochemistry, the subjects of the study will be asked for authorization and their participation will be requested after a detailed explanation of the risks and benefits of the protocol, obtaining signed informed consent.

Obtaining the samples

The universe of the study will be individuals from 19 to 55 years of age with exogenous obesity; they will be recruited in the Obesity Projects area of the Postgraduate Studies and Research section of the Higher School of Medicine of the National Polytechnic Institute, referred by the Comprehensive Medical Service.

Each participant will be asked in writing to enter the study, each one was identified, and a clinical history was prepared with anthropometric measurements: weight, percentage of body fat, percentage of visceral fat, height, BMI. Peripheral blood will also be taken for blood biochemistry and messenger RNA extraction and qPCR tests to determine gene expression of NLRP3, IL-1 β and TNF- α .

Biochemical tests.

Peripheral blood samples will be evaluated by an external laboratory.

Blood samples will be collected at the beginning and three months after treatment. Participants were called at 7 am, after fasting for at least 8 hours, and the sample was collected in Vacutainer tubes (BD, USA), added with ethylenediaminetetraacetic acid (EDTA) to prevent coagulation. 4 mL of blood was taken from everyone; from there, 1 mL of Trizol (Sigma-Aldrich, USA) was added to 2 2 mL tubes with 100 μ L per tube. The blood was vortexed for 30 s and stored at -70 °C until processing. The rest of the blood was stored at -20 °C.

Anthropometric evaluation

The somatometry of each participant will be determined by wearing light clothing and without shoes: weight, height, % body fat, % visceral fat.

Height

It will be defined as the distance between the vertex and the support plane.

- Instrument: Stadiometer (Seca mod. 208).
- The measurement will be expressed in cm with a precision of 1 mm.

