The thermocycler was programmed with the following scheme: preincubation for one cycle of 10 minutes at 95°C; the reaction for 45 consecutive cycles (denaturation at 95°C for 10 seconds, annealing at 60°C for 30 seconds and extension at 72°C for 1 second) and the final incubation at 40°C for 30 seconds.

Table 5. Oligonucleotide sequences used to determine gene expression.

Gen	Proteins	Sequences	Concentration
NLRP3	Proteína 3 que contiene dominios NACHT, LRR y PY	F: 5' GCA AGA CTT TGA CAA CAT GC3' R: 3'CAC CTG TTG TGC AAT CTG AAG5'	10nM
TNF- α	Factor de necrosis tumoral alfa	F: 5' CAGCCTCTCTCCCTTGAT3' R: 3'GCCAGAGGGCTGATTAGAGA5'	10nM
IL-1 β	Interleucina 1 beta	F: 5' TTG GGT AAT TTT TGG GAT CTT AC3' R: 3'CTG TCC TGC GTG TTG AAA GA5'	10nM
B-actina	Gen constitutivo	F: 5' AGC CAC ATC GCT CAG ACA C3' R: 3'GCC CAA TAC GAC CAA ATC C5'	10nM

Statistical analysis

The values of each determination are expressed as the mean \pm SE. The differences between the groups were calculated with ANOVA. Differences between the groups will be determined by using Student's T test. In all tests, a value less than or equal to 0.05 was considered significant.

Ethical aspects

The study will be of lower than minimum risk, since no blood was obtained from the participants in quantities greater than the limit established by the Regulations for Research on Human Beings of the General Health Law. The project was evaluated,

approved and accepted by the Research and Ethics Committee of the Higher School of Medicine of the National Polytechnic Institute.

The study was carried out in accordance with the ethical principles:

- Declaration of Helsinki of the WMA - Ethical principles for medical research involving human beings¹²⁶.
- Written and signed informed consent as stipulated in article 21 of the General Health Regulations on Health Research¹²⁷.
- As stipulated in article 17 of the General Health Regulations on Health Research, this project is classified as minimal risk¹²⁷.
- The protocol was carried out in compliance with the recommendations established in NOM-087-ECOL-SSA1-2002, which addresses matters related to Environmental Protection and Environmental Health; Biological-infectious Hazardous Waste¹²⁸.

Material Resources

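### The analysis plan does not name the Group 3 versus Group 2 comparison or use the baseline expression sample; a baseline-adjusted comparison of those two groups would use data already planned

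*Combined protocol and SAP*

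**What the plan says.** Under Statistical analysis, two sentences name tests: "The differences between the groups were calculated with ANOVA", and "Differences between the groups will be determined by using" Student's t test. Results are summarised as mean ± SE, and 0.05 or less counts as significant in every test. No pair of groups, time point, change score, paired test or covariate is given.

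Other sections supply what a specific analysis would need:

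- **Question.** The general objective and the hypothesis (sections 9 and 10) concern berberine's effect on expression of NLRP3, IL-1β and TNF-α. The only expression comparison that the objectives name is obese versus control subjects (specific objective 5).
- **Groups.** Study groups lists "Group 2. Individuals with exogenous obesity: nutritional plan intervention, moderate controlled aerobic exercise for lifestyle change" and "Group 3. Individuals with exogenous obesity: nutritional plan intervention, moderate aerobic exercise and Berberine phytopharmaceutical". Group 1 has the nutritional plan only, and Group 4 is normal-weight without intervention.
- **Samples.** Under Obtaining the samples: "Peripheral blood will also be taken for blood biochemistry and messenger RNA extraction and qPCR tests to determine gene expression". Under Biochemical tests: "Blood samples will be collected at the beginning and three months after treatment". The latter paragraph also describes the Trizol aliquots, so its timing covers the RNA samples.
- **Formation of groups.** Variable Description gives consecutive, non-probabilistic sampling and "Observation method: open". Of participants, Study groups says "they were informed of the intervention and the group to which they belonged". No randomisation is described.

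**The concern.** Four groups give 4 × 3 / 2 = 6 possible pairs, and the plan does not say which pair answers the berberine question. Apart from the word for controlled exercise, which appears only in the Group 2 entry, Groups 2 and 3 have the same listed background and differ by berberine. Group 3 against Group 1 mixes berberine with exercise. Any comparison with Group 4 mixes it with obesity and the whole programme. So only Group 3 versus Group 2 isolates berberine, as an open add-on effect.

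The design is described as longitudinal and baseline expression is to be measured, but the analysis text gives the baseline no role. With groups formed consecutively, Groups 2 and 3 may differ in expression before treatment. A comparison of 3-month values alone would attribute what remains of that difference to berberine, and would usually be less precise than it could be.

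**Working it through.** The documents give no SD, effect size, correlation, power or per-group number, so there is no planned figure to reproduce. Everything below is illustrative.

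**Inputs**

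- From the documents: 90 obese patients, 30 controls, significance at 0.05.
- Assumed: 90/3 = 30 per obese group with complete pairs, two-sided tests, equal SDs, a true Group 3 minus Group 2 difference of 0.5 SD, and correlation ρ between baseline and 3-month expression of 0.3, 0.5, 0.6 or 0.7.

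**Step 1: power for one gene.** For 3-month values the standard error is √(2/30) = 0.258 SD, so the noncentrality is 0.5/0.258 = 1.94 on 58 df. The other methods multiply the variance by:

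- change from baseline: 2(1 − ρ), 58 df;
- ANCOVA: (1 − ρ²)(1 + 1/(2n − 4)), 57 df. The second factor allows for chance baseline imbalance; at n = 30 it is 57/56.

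Example at ρ = 0.5: the ANCOVA factor is 0.75 × 57/56 = 0.763, the noncentrality is 1.94/√0.763 = 2.22, and power is 58.7%.

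| ρ | 3-month t test | Change score | ANCOVA |
|---|---|---|---|
| 0.3 | 48% | 36% | 51% |
| 0.5 | 48% | 48% | 59% |
| 0.6 | 48% | 57% | 66% |
| 0.7 | 48% | 69% | 75% |

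**Step 2: where the gain ends.** ANCOVA and the 3-month test have equal variance when (1 − ρ²) × 57/56 = 1, that is ρ² = 1/57, or ρ = 0.13. At ρ = 0, ANCOVA has 47.1% power against 47.8%, a loss of 0.7 points. If 10% of baseline samples were unusable, ANCOVA on 27 pairs per group at ρ = 0.3 has about 47%, against 48% for a 3-month test that keeps all 30.

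**Step 3: false positives with a 0.5 SD baseline gap and no effect** (simulation). Two ways for the gap to evolve were examined.

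*(a) The gap carries forward only through ρ.* Expected bias is 0.5ρ for the t test, zero for ANCOVA and −0.5(1 − ρ) for change.

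*(b) The gap persists unchanged.* Expected bias is 0.5 for the t test, 0.5(1 − ρ) = 0.35/0.25/0.20/0.15 SD for ANCOVA, and zero for change.

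| ρ | (a) t test | (a) ANCOVA | (a) Change | (b) t test | (b) ANCOVA | (b) Change |
|---|---|---|---|---|---|---|
| 0.3 | 9% | 5% | 20% | 48% | 27% | 5% |
| 0.5 | 16% | 5% | 16% | 48% | 19% | 5% |
| 0.6 | 21% | 5% | 14% | 48% | 15% | 5% |
| 0.7 | 27% | 5% | 11% | 48% | 12% | 5% |

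ANCOVA has fewer false positives than the 3-month test in every row. Neither ANCOVA nor the change score holds 5% under both (a) and (b), and the documents do not say which applies.

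**Step 4: requiring both analyses to be significant in the same direction.** Power for 0.5 SD becomes 32/44/53/66%, which is below the t test's 48% at ρ = 0.3 and 0.5. False positives fall to about 2–3%, with or without a baseline gap.

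**Step 5: the four-group F test.** If only Group 4 differs, by 0.5/0.8/1.0 SD, F on 3 and 116 df is significant 48/89/98% of the time with no berberine effect.

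**The case against.** The best reply is that the comparator is inferred. The plan does not say that its t test uses 3-month values. With paired samples and a longitudinal design, a t test on change fits the text equally well. This stands. If change was meant, ANCOVA still gains power across the range examined, but its advantage in bias holds only under (a) and reverses under (b).

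Second, the gain is not guaranteed. It depends on an unknown ρ, is small at 0.3, is absent below about 0.15, and can be cancelled by lost baseline samples. The protocol itself eliminates contaminated, lysed or clotted samples and sets an RNA purity window. This stands too.

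Third, the existing test sentences cover every comparison, so deleting them would leave Group 1 and specific objective 5 without a test. That argues for adding text rather than replacing it. Likewise, a rule that calls the result inconclusive whenever the two analyses disagree would give the change score a veto, at the power cost in step 4.

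A reader might also infer that the plan has decided to ignore baseline, or that it treats the four-group ANOVA as its test of berberine. The documents support neither: they are silent on both, and step 5 matters only if such an F test were presented that way. Nor does baseline adjustment make non-randomised groups comparable; it deals only with the measured baseline of that gene.

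**Conclusion.** The point holds as an omission with a cheap remedy, and it should be fixed. The plan's main question has no named contrast, no time point and no stated use of the baseline expression sample. Against an unadjusted 3-month t test, ANCOVA of Group 3 versus Group 2 raises power for 0.5 SD from 48% to about 51–75% over ρ = 0.3 to 0.7. It also reduces, but does not always remove, false positives from a pre-existing gap. Those sizes rest on 30 complete pairs per group, equal SDs and an assumed ρ. Against a change-score test, the claim is limited to precision. Since the documents do not settle how a baseline gap would carry forward, both estimates should be shown, with one named as primary. Confounding other than through baseline expression may remain under either analysis.

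**What to change.** Keep the ANOVA and t test sentences for the other comparisons, including those with Group 1 and obese versus control subjects for specific objective 5. Add:

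> The berberine comparison is Group 3 versus Group 2. For each gene, 3-month relative expression (preferably log2) is analysed by ANCOVA with group and that gene's baseline expression as terms. The adjusted difference with its 95% CI is the primary estimate, tested at the 0.05 level. The Group 3 versus Group 2 difference in change from baseline, with its 95% CI, is reported alongside as a sensitivity analysis. It does not decide significance; any material difference between the two estimates is stated as uncertainty due to non-random groups. A four-group F test is not read as evidence about berberine. Groups were formed consecutively and treatment was open, so confounding may remain. If expression data were analysed before this change, the analysis is labelled post hoc.

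The last sentence is needed because the Abstract already reports anthropometric and biochemical results and says that expression data were obtained.

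**Cost.** No new samples, visits or patients; one degree of freedom; and participants without a usable baseline sample leave the ANCOVA. If the sponsor prefers to require both analyses to agree, the plan should state the price: power 32/44/53/66% and a false-positive rate of about 2–3% instead of 5%. Multiplicity over the three genes is a separate decision that this wording does not settle.
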